### 20.3 Declaration of Helsinki

This study will be conducted in accordance with the ethical principles that have their origin in the Declaration of Helsinki and that are consistent with good clinical practice (GCP) and the applicable regulatory requirements.

## 20.4 Participant Confidentiality

To maintain participant confidentiality, all study documents and files will use an anonymous study identification number to identify participants and only the study coordinator will maintain linkages, and have access to, subject identities. Local computer storage of data is password protected and located within a hospital- or institute-based firewall. Study data will be stored in the clinical research office at the Lois Pope Life Center.

The Data Safety Monitoring Plan to maintain confidentiality is as follows.

- a. The data will be stored for at least ten (10) years.
- b. All physiologic and neuropsychological data is coded with a unique identifying number, different from the subject's medical record number or social security number, to maintain confidentiality, in order for these to be matched to the samples. The study coordinator is responsible for maintaining this code. The demographic information of the subject initially required to code with is password protected on his/her computer and is within a locked office.
- c. All signed consents and study data are stored within a locked filing cabinet in a locked office for which the PI will have oversight. Only personnel listed on study protocols will have access to study data. However, pertinent study data will be shared with a subject in cases where the subject could possibly benefit medically or otherwise from the data, or upon their request.
- d. Any findings that increase risks to participants will also be shared with all study participants.
- e. Study data will also be made available to the Funding Sponsor, The Miami Project to Cure Paralysis and the FDA for audit.
- f. Study data may also be made available to consultants hired by the Miami Project to Cure Paralysis/Miller School of Medicine bound by written confidentiality for the specific purpose of providing oversight on the project.

## 21 DATA HANDLING AND RECORDKEEPING

### 21.1 Case Report Forms

- a. Where possible, data will be documented in source documents initially and then recorded on CRFs. Dark indelible-ink pens (preferably black-ink ballpoint pens) shall be used.
- b. The originals of the CRFs plus one additional copy must be returned to the Sponsor; the PI must retain a copy of the CRFs for his/her file.
- c. CRFs and other pertinent records are to be submitted to the Sponsor during and/or at completion or termination of the study.
- d. The Investigator also must submit all incomplete CRFs that document patient experience with the study device, including retrievable data on patients who withdraw before completion of the study.
- e. Laboratory results and ECG results will be processed using electronic data provided from the centralized organizations and directly submitted to the data management group. Any additional types of data that will be recorded directly into the CRF shall be listed in Section 10.3.8 of this protocol.

### 21.2 The Study Coordinator

The PI will monitor the progress of the research study with the assistance of a Study Coordinator. Data will be entered into Case Record Forms (CRF) at the study site within 5 days of the data time-

point, and the Study Coordinator will review the accuracy of the entered data by comparison with participants' medical records within thirty (30) days. Potential discrepancies will be flagged and checked/corrected by study site personnel.

### 21.3 Adverse Event Reporting

The Investigator agrees to report all AEs to the Sponsor as described in the Adverse Events Reporting section, Appendix 1. Furthermore, the Investigator is responsible for ensuring that any Co-investigator or Sub investigator promptly brings AEs to the attention of the Investigator. The Investigator also is responsible for informing the participating IRB/IEC of any SAEs.

### 21.4 Protocol Amendments

- a) Any significant change in the study protocol will require an amendment. In addition, major modifications to the research protocol and any modifications that could potentially increase risk to participants will be submitted to the FDA for approval prior to implementation.
- b) The Investigator and the Medical Monitor indicate their approval of significant changes to the protocol or CRFs by signing the approval page of the amendment. Once the Sponsor has approved a protocol amendment, the Investigator shall submit it to the IRB/IEC for written approval. The Sponsor submits a copy of the protocol amendment to the appropriate regulatory agency/agencies. A protocol amendment may be implemented after it has been approved by the IRB/IEC.
- c) A protocol change intended to eliminate an apparent immediate hazard to patients may be implemented immediately, but the change must then be documented in an amendment, reported to the IRB/IEC within five (5) working days, and submitted to the appropriate regulatory agency in the required time frame.
- d) Minor amendments (including minor changes to CRFs) will be submitted with the continuing review report to the UM HSRO for acceptance.

### 21.5 Final Study Report

- a) The Investigator must complete a report notifying the IRB/IEC of the conclusion of the clinical study. This report should be made within three (3) months of completion or termination of the study.
- b) The final report sent to the IRB/IEC must also be sent to the Sponsor and, along with the completed CRFs, constitutes the final summary to the Sponsor, thereby fulfilling the Investigator's regulatory responsibility.

### 21.6 Records Retention

- a) The Investigator shall retain and preserve one copy of all data generated in the course of the study, specifically including but not limited to those documents defined by GCP as essential documents, for the longer of: (a) 2 years after the last marketing authorization for the study drug has been approved or the Sponsor has discontinued its research with respect to such drug or (b) such longer period as required by applicable global regulatory requirements.
- b) At the end of such period, the Investigator shall notify the Sponsor of the intent to destroy all such material.
- c) The Sponsor shall have 30 days to respond to the Investigator's notice, and the Sponsor shall have a further opportunity to retain such materials at the Sponsor's expense.

## 22 FINANCING AND INSURANCE REGARDING PATIENT INJURY

In general, if a patient is injured as a direct result of the study device, the Sponsor will pay for reasonable and necessary medical treatment for the injury, to the extent the expenses are not covered by the patient's medical insurance, a government program, or other responsible third party. If laws or regulations of the locality in which the trial is taking place require additional payment of expenses, the Sponsor shall comply with such law or regulation. Where applicable, the Sponsor will take specific national insurance.

## 23 PUBLICATION POLICY

All data will be summarized and analyzed. The Principal Investigators will prepare a clinical narrative. The Principal Investigators will prepare abstract submissions to an appropriate research meeting and a manuscript for submission to a peer-reviewed journal. The publication policies of The Miami Project to Cure Paralysis and Miller School of Medicine follow those recommended by the Association of American Medical colleges and the Institute of Medicine. The trial will be fully registered according to International Committee of Medical Journal Editors (ICMJE) standards within 21 days of its outset in <http://clinicaltrials.gov/>.

## 24 APPENDICES

- 24.1 Appendix 1 - Description of Adverse Event Reporting (following page)
- 24.2 Appendix 2 – Protocol References

### 24.1 APPENDIX 1 -- ADVERSE EVENTS REPORTING

#### 1. Definitions

- 1.1. An **Adverse Event (AE)** [a.k.a. "adverse experience"] is any untoward, undesired, unplanned clinical event in the form of signs, symptoms, disease, or laboratory or physiological observations

occurring in a human being participating in a clinical study with a Sponsor study device, regardless of causal relationship. This includes the following:

- Any clinically significant worsening of a preexisting condition.
- Any recurrence of a preexisting condition.
- An AE occurring from excessive output of a Sponsor study device whether accidental or intentional (i.e., an amplitude higher than that prescribed by a clinical neurophysiologist).
- An AE that has been associated with the discontinuation of the use of a Sponsor study device.

Note: A medical procedure is not an AE, but the reason for a procedure may be an AE.

- 1.2. A **Preexisting Condition** is a clinical condition (including a condition being treated) that is diagnosed before the patient signs the informed consent form and that is documented as part of the patient's medical history.

The questions concerning whether the condition existed before the start of the active phase of the study and whether it has increased in severity and/or frequency are used to determine whether an event is a treatment-emergent AE (TEAE). An AE is considered to be treatment emergent if:

- it was not present when the active phase of the study began and is not a chronic condition that is part of the patient's medical history, or
- it was present at the start of the active phase of the study or as part of the patient's medical history, but the severity or frequency increased during the active phase. The active phase of the study begins at the time of the first use of the study device.

- 1.3. A **Serious Adverse Event (SAE)** is any AE occurring at any dose (voltage output) that results in one (1) or more of the following outcomes:

- Death.
- Life threatening situation (see below).
- Inpatient hospitalization or prolongation of an existing hospitalization (see below).
- Persistent or significant disability or incapacity (see below).
- Congenital anomaly or birth defect.

Additionally, important medical events that may not result in death, be life threatening, or require hospitalization may be considered SAEs when, based on appropriate medical judgment, they may jeopardize the patient and may require medical or surgical intervention to prevent one of the outcomes listed above. Examples of such events include allergic bronchospasm requiring intensive treatment in an emergency room or at home, blood dyscrasias or convulsions that do not require hospitalization. If there is any doubt whether the information constitutes an AE or SAE, the information is treated as an AE or SAE.

- 1.4. A **Life Threatening Adverse Event** is any AE that places the patient at immediate risk of death from the event as it occurred. A life-threatening event does not include an event that might have caused death had it occurred in a more severe form but that did not create an immediate risk of death as it actually occurred.
- 1.5. **Hospitalization** is to be considered only as an overnight admission. Hospitalization or prolongation of a hospitalization is a criterion for considering an AE to be serious. In the absence of an AE, the participating Investigator should not report hospitalization or prolongation of hospitalization on a CRF. This is the case in the following situations:

- Hospitalization or prolongation of hospitalization is needed for a procedure required by the protocol.
- Day or night survey visits for biopsy or surgery required by the protocol.
- Hospitalization or prolongation of hospitalization as part of a routine procedure followed by the study center (e.g., stent removal after surgery).
- In addition, a hospitalization planned before the start of the study for a preexisting condition that has not worsened does not constitute an SAE (e.g., elective hospitalization for a total knee replacement due to a preexisting condition of osteoarthritis of the knee that has not worsened during the study).

1.6. **Disability** is defined as a substantial disruption in a person's ability to conduct normal life functions.

## 2. Timing for Reporting Serious Adverse Events

- 2.1. Any SAE, regardless of causal relationship, must be reported to the Sponsor's Medical Monitor (or a designated affiliate) immediately (i.e., within 24 hrs). A completed Serious Adverse Event Form must be faxed to the number indicated at the front of the clinical protocol no later than 24 hours after the investigator becomes aware of the SAE. A phone call should be made to confirm that the SAE fax was received. Compliance with this time requirement is essential for the Sponsor to comply with regulatory obligations.
- 2.2. Follow-up information relating to an SAE must be reported to a Sponsor Medical Monitor (or an affiliate or designee) within 24 hours of receipt by the Investigator by faxing a completed serious adverse event form to the number indicated in the front of this protocol and confirming by telephone that the fax was received. The patient should be observed and monitored carefully until the condition resolves or stabilizes or its cause is identified.
- 2.3. Any emergency must be reported to a Sponsor Medical Monitor (or an affiliate or designee) immediately (within 24 hours) by contacting a Medical Monitor listed in the front of this protocol.
- 2.4. For all other inquiries and information about this study, contact Miami Project to Cure Paralysis at the phone number listed in the front of the clinical protocol.

## 3. Reportable Events/Information

- 3.1. An AE or SAE that occurs between the time that the patient signs the informed consent form through thirty (30) days from the patient's last dose (voltage output), regardless of study device or protocol relationship should be reported. This includes events that emerge during the screening and pre-treatment run-in periods.
  - All AEs and SAEs will be recorded on source documents and recorded on CRFs.
  - All AEs and SAEs that occur after the screening period will be recorded on the CRFs.
  - The Sponsor Medical Monitor must instruct the investigator to follow up as is medically necessary on all AEs, SAEs, and other reportable events until the event has subsided or values have returned to baseline, or in case of permanent impairment, until the condition stabilizes.
- 3.2. For SAEs: The investigator will provide all documentation pertaining to the event (e.g., additional laboratory tests, consultation reports, discharge summaries, postmortem reports, etc.) to the Sponsor Medical Monitor in a timely manner. Reports relative to the patient's subsequent course must be submitted to the Sponsor until the event has subsided or, in case of permanent impairment, until the condition stabilizes.

4. **Post-study SAEs related to device** include any abnormal biological or vital signs values that are considered clinically relevant by the Investigator. These must be reported in the same time frame and following the same process as for an AE or an SAE

4.1. The Investigator managing the excessive voltage may order any additional test(s) he or she thinks is necessary to manage the patient properly.

#### 5. Recording and Reporting

5.1. At each required study visit, all AEs that have occurred since the previous visit must be documented and recorded in the Adverse Event Record of the patient's CRF. The information recorded should be based on the signs or symptoms detected during the physical examination and clinical evaluation of the patient. In addition to the information obtained from those sources, the patient should be asked the following nonspecific question: "How have you been feeling since your last visit?" Signs and symptoms should be recorded using standard medical terminology.

5.2. The following AE information must be included (when applicable):

- the specific condition or event and direction of change;
- whether the condition was preexisting (i.e., an acute condition present at the start of the study or history of a chronic condition) and, if so, whether it has worsened (e.g., in severity and/or frequency);
- the dates and times of occurrence; severity; causal relationship to study device; action taken; and outcome.

5.3. The causal relation between an AE and the study device will be determined by the investigator on the basis of his or her clinical judgment and the following definitions:

- **Definitely related:** Event can be fully explained by use of the study device.
- **Probably related:** Event is most likely to be explained by use of the study device rather than the patient's clinical state or other agents/therapies.
- **Possibly related:** Event may be explained by use of the study device or by the patient's clinical state or other agents/therapies.
- **Probably not related:** Event is most likely to be explained by the patient's clinical state or other agents/therapies, rather than the study device.
- **Definitely not related:** Event can be fully explained by the patient's clinical state or other agents/therapies.

5.4. When assessing the relationship between use of a study device and an AE, the following should be considered:

- Temporal relationship between use of the study device and the AE.
- Biological plausibility of relationship.
- Patient's underlying clinical state or concomitant agents and/or therapies.

5.5. SAEs that are not study device related may nevertheless be considered by the participating Investigator or the Medical Monitor (or designee) to be related to the conduct of the clinical study, i.e., to a patient's participation in the study. For example, a protocol-related SAE may be related to a procedure required by the protocol.

5.6. The following definitions should be used when determining the severity of an AE. Please note that there are some cases in which removal of study device may be appropriate.

- **Mild (grade 1):** The AE is noticeable to the patient but does not interfere with routine activity. The AE does not require discontinuing use or reducing the voltage output of the

study device.

- **Moderate (grade 2):** The AE interferes with routine activity but responds to symptomatic therapy or rest. The AE may require reducing the voltage output but not discontinuing use of the study device.
- **Severe (grade 3):** The AE significantly limits the patient's ability to perform routine activities despite symptomatic therapy. In addition, the AE leads to discontinuing use or reducing the voltage output of the study device.
- **Life Threatening (grade 4):** The AE requires discontinuing use of the study device. The patient is at immediate risk of death.

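### The adverse event severity grades include a device action, so a severe or life-threatening event with no change to stimulation fits no grade

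*Combined protocol and SAP*

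**What the plan says.** Appendix 1 (section 24.1), item 5.6 introduces the scale with "The following definitions should be used when determining the severity of an AE". No other severity scale is given in the document. Each grade combines a statement about the patient with a statement about the device:

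- Grade 1 (mild): noticeable, with no interference in routine activity. Device clause: "The AE does not require discontinuing use or reducing the voltage output of the" study device.
- Grade 2 (moderate): "The AE interferes with routine activity but responds to symptomatic therapy or rest". Device clause: "The AE may require reducing the voltage output but not discontinuing use of the study device".
- Grade 3 (severe): "The AE significantly limits the patient's ability to perform routine activities despite symptomatic therapy". Device clause: "In addition, the AE leads to discontinuing use or reducing the voltage output of the study device".
- Grade 4 (life threatening): immediate risk of death. Device clause: "The AE requires discontinuing use of the study device".

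Item 5.2 of the same appendix lists what must be recorded for each event, including "the dates and times of occurrence; severity; causal relationship to study device; action taken; and outcome". Severity and action taken are therefore already two separate items.

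**The concern.** Severity should describe how badly the event affected the patient. What the team did to the stimulator is a different fact and has its own field. When the action is part of the grade, an event can be disabling and still fail the definition of severe because nobody had reason to change the stimulation.

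This is a real possibility in this trial. Item 3.1 requires events to be reported from consent onward whether or not they relate to the device or the protocol. Section 10 lists surgical risks such as intracerebral hemorrhage, stroke, seizure, paralysis and infection. Section 15 also expects problems that belong to spinal cord injury itself, for which a voltage change may be irrelevant. Adverse effects are Aim 1 (section 11.1) and safety is part of the primary objective (section 11.3), so severity ought to be recorded correctly.

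**Working it through.** No arithmetic applies. The check reads each grade as a patient condition joined to a device condition and tests events against them.

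**Step 1. Are the conditions joined?** In grade 3 the device clause opens with words of addition, so both parts must hold. In grade 4 the device clause and the risk of death stand as two statements, both part of the definition. In grade 2 the voltage clause is permissive, so a moderate event without a voltage change still fits; only discontinuation is excluded.

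**Step 2. A severe event with no device action.** Take an event that significantly limits activity despite therapy, carries no immediate risk of death, and leads to no voltage reduction or discontinuation.

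| Grade | Patient condition | Device condition | Fits? |
|---|---|---|---|
| 1 | Fails: it interferes with activity | Met | No |
| 2 | Fails: it does not respond to therapy or rest | Met | No |
| 3 | Met | Fails: no device action | No |
| 4 | Fails: no immediate risk of death | Fails: not discontinued | No |

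The event meets 0 of 4 grades.

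**Step 3. A life-threatening event with no device action.** Grade 4 fails on its device clause, grade 3 fails on its own, and grades 1 and 2 fail on the patient condition. Again 0 of 4. Item 1.4 of the same appendix defines a life-threatening event by immediate risk of death alone. One event can therefore be life threatening under item 1.4 and not under item 5.6.

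**Step 4. A trivial event that required a voltage reduction.** Grade 1 excludes it because of the reduction. Grade 2 allows the reduction but asks for interference with activity, which is absent. An investigator who must choose would probably move it up to grade 2.

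**Step 5. Can such events occur?** Table 1 puts lead placement in week 7 and connection in week 8. Section 12.3 starts stimulation 12 to 48 hours after internalization. Apart from test stimulation during surgery (section 14.3.4), there is no ongoing output to reduce in that interval. After it, any severe event unrelated to stimulation may be managed with the settings left alone.

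**Step 6. Where are the grades used?** Section 17.1 plans to list events and compare incidence with historical controls. Its Table 3 is by type of event, without grades. Section 15 sorts events by cause. Sections 12.7 and 13.5 call dysesthesia and neuropathic pain severe among the reasons for removal, but do not refer to the appendix grades.

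**The case against.** The strongest reply is that little depends on these grades. Seriousness (items 1.3 to 1.6) rests on outcome, with no voltage condition, and includes important medical events. A disabling hemorrhage would be a serious adverse event reportable within 24 hours, and item 5.5 provides for procedure-related events. With 12 participants and individual listings, it would not be hidden. All of this stands, and it limits the consequence. It does not supply a grade for the event.

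Four stronger readings are tempting, and the documents do not support them:

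- *Every severe surgical event escapes grade 3.* The clause covers discontinuing use as well as lowering voltage. An infection leading to removal (section 14.4), or a complication that ends test stimulation or prevents internalization (section 14.3.4), can reasonably count as discontinuing use. Only events with no device action are affected.
- *Turning the voltage down makes an event severe.* It cannot, because grade 3 also requires significant limitation despite therapy. The upward distortion is confined to the boundary between grades 1 and 2.
- *Planned severity tables would understate surgical harm.* No such tables are planned. Nor is one participant in 12 (1/12 = 8.3%) a measure of this problem; it is the share that any single participant represents.
- *The scale is defective without a fatal grade.* Death is already a seriousness criterion, and outcome is a required field. A fifth grade is a preference.

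The device clauses may also have been meant as management instructions. That is possible, but item 5.6 presents them as definitions for determining severity.

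**Conclusion.** The point holds in limited form. As written, a severe or life-threatening event with no device action has no valid grade, and a trivial event that required a voltage reduction cannot be grade 1. The result is missing or misplaced values in a required field, and errors in any later summary by grade. Capture of serious events, the planned incidence comparison and the stopping provisions are unaffected. The documents give no basis for estimating how many events would be affected.

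The conclusion assumes that investigators apply item 5.6 literally. Those who disregard the device clauses will grade sensibly but depart from the protocol, and may do so inconsistently. This is a drafting error worth correcting, and it does not threaten the trial's main conclusions.

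**What to change.** In Appendix 1, item 5.6, define grades 1 to 4 by the functional and clinical effect of the event alone, and remove the voltage and device-use clauses from the definitions. Record any reduction, discontinuation or removal only in the action-taken field of item 5.2. State that the same grades apply to surgical, pre-stimulation and device-unrelated events, and align grade 4 with item 1.4.

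If the device clauses were intended as management instructions, state them apart from the severity definitions and reconcile them with section 15, which ties discontinuation of study treatment to the cause of an event. Nothing here calls for a change to any stimulation or stopping rule. A fatal grade may be added but is not needed.

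The cost is an edit to one appendix paragraph and the matching case report form instructions, with no new data collection. For events already recorded, grades can be checked against the event description and the action-taken entry.
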